7.1.4. Drop-out criteria

After screening and prior to treatment any changes in the patient's medical condition should be assessed. The patient should be excluded from treatment if these changes represent deterioration in his/her condition which may affect the patient's safety and/or suitability for the study (e.g. exclusion criteria).

Throughout the course of a subject's participation in the study, he/she may be removed from the study as follows:

- Whenever it is necessary to safeguard his/her welfare as judged by the Principle Investigator,
- Participation in another investigational drug trial,
- Subjects who express a desire to withdraw from the study,
- Subjects with EAR identified post randomization but prior to treatment.

The reason for any subject withdrawal from the study should be recorded in the eCRFs and the occurrence should be reported to the sponsor. Early termination visit should include final assessments as in the Hospital Discharge visit, as applicable (please refer to Section 8.7 of the study protocol).

Discontinued subjects will not be replaced.

When a subject is removed from the study treatment, he/she will receive treatment according to the standard of care as appropriate in the investigative site and will be followed up according to the study schedule, in accordance with patient's availability.

7.1.4.1. *Stopping rules (apply for NexoBrid or Gel Vehicle arms only)*

Treatment (eschar removal) should be stopped following a safety concerns raised by the treating physician or if a patient expresses his desire to withdraw from the study. In addition, in the following situations:

Burn Induced Compartment Syndrome (BICS) Monitoring and Diagnosis

All circumferential wounds should be closely monitored during treatment for signs of improvement or deterioration that may require escharotomy. If clinical assessment and SpO₂ monitoring are possible, they will be done continuously and recorded in the eCRFs every 2 hours. If such assessment is not practical, direct pressure will be measured every 2 hours from start of the eschar removal. The eschar removal process shall be discontinued (escharotomy may be performed at the discretion of the physician in any of the following cases:

- Increasing interstitial/compartment pressure >30 mmHg
- Difference of >20 mmHg of diastolic pressure between the opposite uninjured extremity

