- Decreased SpO₂ reading during treatment with difference of >6% compared to a non injured extremity or deterioration of clinical signs
- Deterioration of any of the 5 “P” signs: Pain, Paralysis, Pulselessness, Pallor, Paraesthesia

Since in such cases the eschar removal procedure will not be completed as planned, such patients (if any) will still be part of the full analysis set (FAS, see Definition in Appendix 13.1.1) and any missing data usually collected during eschar removal (e.g. time to end of eschar removal, etc.) will be handled as missing data according to the protocol.

In case of 3 consecutive cases where there is a need to disrupt the dressing and perform a surgical escharotomy, enrollment will be halted and a DSMB shall be convened to:

- assess the severity of the phenomenon in a closed session
- Recommend on appropriate corrective measures, as applicable to prevent such reoccurrences

As discussed above, increased interstitial/compartment pressure is a common medical condition in circumferential deep burns and its detection and resolution is part of daily standard of care. The only difference in the treatment of the patients in the study is during the eschar removal stage as dictated by randomization.

Coagulopathy during or within 24 hours of eschar removal

It is evident that during the first 48 hours post injury there is deterioration in coagulation parameters in burn patients [22]. In addition, some burn patients are treated with

anticoagulants after admission (in some burn centers all patients are treated with anticoagulants). Due to these facts, any stopping rule concerning coagulopathy after topical debriding agent application must take these factors into consideration.

Enrollment will be halted and a DSMB will convene if 3 subjects develop the following signs which have been defined as life threatening coagulopathy in trauma patients:

INR>2 or a PTT>2 times the normal range [23], in cases where the patient is not receiving anticoagulants that can explain the coagulopathy.

A DSMB shall be convened to assess in a closed session the following:

- The relationship between coagulopathy and the treatment arm
- The severity of the phenomenon
- Recommend on appropriate corrective measures, as applicable to prevent such reoccurrences

DSMB investigation will consider patients' medical history, including any anticoagulants given to the patient prior to start of treatment.

Post treatment diagnosed infection (until complete wound closure)

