9.5. Full analysis Set (Intent-to-Treat population)

The full analysis set (FAS) includes all patients who are randomized into the trial. The analysis is focused on the planned treatment.

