10.1.1. Primary Endpoint: Incidence of complete eschar removal

Little or no missing data are expected for the primary endpoint, since the outcome is assessed only several hours after the start of treatment for both NexoBrid and Gel Vehicle groups. The main analysis will be a complete-case analysis. In each treatment group, only patients with documented total eschar removal (at the end of the eschar removal soaking period) will be counted and this number divided by the total number of complete cases.

Three sensitivity analyses will be conducted for this endpoint. A first analysis will count all patients with missing data (for this endpoint) as positive (i.e. complete eschar removal) and a second analysis will count all patients with missing data as negative (i.e. no complete eschar removal). The third sensitivity analysis will be a tipping point analysis, in which the effect of missing data on the conclusion will be investigated. This analysis will be conducted as follows:

1. Impute the entries of the incomplete data sets $m = 100$ times from Bernoulli distributions. For the imputations of the Gel Vehicle group, the event probability p is chosen as the observed incidence of complete eschar removal in the Gel group (without missing data). For the NexoBrid group the event probability will be $p = p_{obs} - s$, where s is a shift parameter (see below). The random seeds for the imputations will be 14983,...,15082.
2. For each of the 100 imputed data sets compute Fishers exact test and calculate the proportion of tests that reject the null-hypothesis.
3. Repeat steps 1. and 2. for $s = 0, 0.05, \dots$ as long as $p_{obs} - s$ is still non-negative.

The analysis outlined here allows investigating for which assumed success probability for the patients with missing data in the NexoBrid group, the conclusion of the analysis remains stable.

Secondary Endpoints

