10.3.5. Exploratory Analyses

10.3.5.1. %SPT area

For each patient the % SPT area (the area of SPT as a percentage of the total area of all TWs) will be calculated. From this a binary variable will be computed indicating whether % SPT area is $< 25\%$ or $\geq 25\%$. Cumulative and absolute frequencies for each category will be computed.

10.3.5.2. %TBSA

A binary variable indicating whether total %TBSA of all TWs is $\leq 15\%$ or $> 15\%$ will be calculated per patient. For this variable cumulative and absolute frequencies for each category will be computed.

10.3.5.3. *Application data*

For the patients of the NexoBrid and the gel vehicle arm the number of applications (0, 1, 2) will be determined. Cumulative and absolute frequencies will be computed for each category. Furthermore, for each patient the amount of NexoBrid gel each patient in the NexoBrid treatment arm has been exposed to, will be calculated.

10.3.5.4. *Maintenance of complete wound closure*

For each follow-up visit the information of complete wound closure for each TW will be aggregated to a binary variable indicating maintenance of complete wound closure on a patient level (i.e. complete wound closure for each TWs of a patient). Cumulative and absolute frequencies will be computed for each category.

10.3.5.5. *% wound area surgically excised for eschar removal*

% of wound area surgically excised for eschar removal, A_{total} , will be calculated using the following formula:

$$A_{total} = \frac{\sum_i (a_i * \%TBSA_i)}{\sum_i \%TBSA_i}$$

where $\%TBSA_i$ is the area of TW i (in % TBSA) and a_i denotes the % of wound area surgically excised for eschar removal of TW i.

10.3.5.6. *Incidence of reduction in interstitial/compartment pressure in circumferential extremities target wounds*

Interstitial/compartment pressure in circumferential extremities target wounds is measured within 1 hour (+30 min) prior to start of each eschar removal procedure and post-eschar removal. For each circumferential target wound and each eschar removal procedure a binary (yes/no) variable will be computed indicating whether reduction in interstitial/compartment pressure in that wound was present.

10.3.5.7. *POSAS*

The Patient Observer Scar Assessment Scale (POSAS) consists of two parts: a patient scale and an observer scale. Both scales contain six items that are scored numerically with 1-10. For each wound of a patient the total score of the patient scale will be computed as:

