11.1.2. Primary Efficacy variable

The primary efficacy variable will be analyzed using the FAS.

The proportions of patients who reached complete eschar removal at the end of the topical agent soaking period will be compared using logistic regression. The primary analysis will be based on the binary variable (yes/no): 'has complete eschar removal been achieved in all TWs' and will compare NexoBrid with the Gel Vehicle (for further definition and explanation of complete eschar removal see Section 1.1 of the protocol and Section 10.3.2 of this SAP). For handling of missing data see Section 10.1.1. The statistical test will be based on Fisher's exact test because of the small numbers expected in the Gel vehicle group. The odds ratio of achieving complete eschar removal for NexoBrid versus Gel Vehicle and its 95% confidence interval will be estimated using exact distribution methods and will be displayed as shown in Table 6. Bar plots will be shown for the proportions of patients who reached complete eschar removal.

If numerically possible, the comparison will supportively be adjusted for the stratification factor wound depth (all TWs full thickness, mixed TWs, all TWs deep partial thickness) by including

the factor in a logistic regression model together with the treatment variable (NexoBrid vs. Gel Vehicle). Similarly, if convergence of the estimation procedure can be obtained, then, in two other supportive analyses, the factor “Total %TBSA per patient” and the factor treatment center group (see Section 13.8.5 of the protocol as well as Section 11.1.7 of this SAP) will be included in a logistic regression model with the treatment variable. Statistical inference will be based upon exact distribution methods using the “exact” statement in the SAS procedure PROC LOGISTIC. The estimated regression coefficients of the regression analyses will be presented as displayed in Table 7.

The odds ratio of achieving complete eschar removal for NexoBrid versus Gel Vehicle will be estimated from these supportive models, as well as 95% confidence intervals and the level of statistical significance. The results will be displayed as shown in Table 6.

The primary efficacy analysis will be repeated on a wound level as an additional analysis using a mixed logistic regression model with a random effect for patient.

Furthermore, as an additional sensitivity analysis, the primary analysis will be repeated using the PP as analysis population.

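### The main primary analysis is assigned to all randomised patients but divides by complete cases, so topical-arm patients without an end-of-soaking assessment drop out and the NexoBrid rate rises relative to the all-randomised rate

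*SAP*

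**What the plan says.** - **Analysis set.** Section 9.5: "The full analysis set (FAS) includes all patients who are randomized into the trial", analysed by planned treatment. Section 11.1.2: "The primary efficacy variable will be analyzed using the FAS".
- **Main handling of missing results.** Section 10.1.1: "The main analysis will be a complete-case analysis". Documented successes "will be counted and this number divided by the total number of complete cases". The stated reason is that the outcome is assessed within hours, so little or no missing data are expected.
- **Stopped patients.** Section 7.1.4.1, on compartment-syndrome stops in the topical arms: "such patients (if any) will still be part of the full analysis set", and any missing data usually collected during eschar removal "will be handled as missing data according to the protocol".
- **Patients never treated.** Section 7.1.4 lists among the reasons for removal from the study: "Subjects with EAR identified post randomization but prior to treatment". Section 10.3.5.3 provides for topical-arm patients with no application: "the number of applications (0, 1, 2) will be determined". Neither section says how such patients enter the primary analysis.
- **Withdrawals.** Section 10.2 keeps withdrawn subjects in the full analysis set and refers to section 10.1 for imputation of their missing values.
- **Sensitivity analyses.** Section 10.1.1 plans three for this endpoint: all missing counted as success, all missing counted as failure, and a tipping-point analysis that lowers the assumed NexoBrid success probability in steps of 0.05.

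**The concern.** The set named for the primary analysis and the denominator actually used differ whenever a randomised topical-arm patient has no end-of-soaking assessment. The argument that assessment follows within hours covers patients who go through application and soaking. It does not cover those whose application is broken off or never begins.

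The endpoint asks whether the topical agent achieved complete removal in all target wounds by the end of the last soaking (sections 7.3.2.1 and 10.3.2). A patient without that assessment has no documented success, yet the main analysis leaves the patient out instead of counting a non-success. What is at stake is the headline NexoBrid rate and the odds ratio against Gel Vehicle. An arm with many successes gains from a smaller denominator, while an arm with almost none barely moves.

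**Working it through.** **The plan's own figure first.** Inputs from section 9.1.1: NexoBrid 0.5665, Gel Vehicle 0.10, Fisher's exact test, two-sided 5%, 65 versus 13 patients. Power is the sum of the binomial probabilities of all tables with a Fisher p-value of at most 0.05. The result is 90.8%, against about 90% stated, so the figure is reproduced. At the planned 75 versus 25 (section 9.3.1) the same calculation gives 99.5%.

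**How the rules combine for a patient without an end-of-soaking result**

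| Step | Section | Consequence |
|---|---|---|
| In the full analysis set? | 9.5, 7.1.4.1 | Yes |
| Primary analysis on that set? | 11.1.2 | Yes |
| In the main denominator? | 10.1.1 | No, complete cases only |
| Missing value imputed? | 10.2 refers to 10.1 | Not in the main analysis |

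**Effect on the rate.** Let x be documented successes, n randomised patients, and d patients without the assessment.

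- All-randomised rate, missing counted as failure: x/n
- Complete-case rate: x/(n − d), which exceeds x/n whenever d > 0 and x > 0

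The SAP gives no value for d. I assume d = 3 or 5, and extend the range to 8. I take x = 42 of n = 75, close to the planning rate (0.5665 × 75 = 42.5).

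| d of 75 | All-randomised | Complete-case | Shift (points) |
|---|---|---|---|
| 3 | 42/75 = 56.0% | 42/72 = 58.3% | +2.3 |
| 5 | 42/75 = 56.0% | 42/70 = 60.0% | +4.0 |
| 8 | 42/75 = 56.0% | 42/67 = 62.7% | +6.7 |

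**Gel Vehicle.** The planning range is 0 to 10%. With an assumed 2 successes of 25, losing one patient moves 2/25 = 8.0% to 2/24 = 8.3%. With no successes the rate stays at 0.

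**Odds ratio.** Against an assumed 2/25 in Gel Vehicle with none missing there, the sample odds ratio is (42/33)/(2/23) = 14.6 over all randomised patients. In complete cases it is (42/30)/(2/23) = 16.1 for d = 3 and (42/28)/(2/23) = 17.3 for d = 5.

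**Does the test result depend on the choice?** Fisher's p is 1.6 × 10⁻⁵ for 42/75 versus 2/25 and 4.4 × 10⁻⁶ for 42/70 versus 2/25.

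For power, take 0.5665 as the rate among assessed NexoBrid patients, count 5 of 75 as failures, and keep Gel Vehicle at 0.10 with none missing. The all-randomised NexoBrid rate is then 0.5665 × 70/75 = 0.529, and exact power at 75 versus 25 is 98.7%.

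**The case against.** The strongest reply is that section 10.1.1 already specifies the analysis asked for. Missing-as-failure yields the all-randomised rate, and the missing-as-success and tipping-point analyses examine the same weakness from other sides. That stands: the estimate is not left unprotected, and the remaining issue is which analysis carries the headline.

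Second, a reader might infer that every stopped patient is excluded. The text does not support this. Section 7.1.4.1 speaks of any missing data, gives a timing variable as its example, and covers compartment-syndrome stops only. No section says that a stopped patient goes unassessed. One whom the blinded assessor still rates as incomplete is a documented failure and stays in the denominator.

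Third, the never-treated group is an inference from sections 7.1.4, 10.1.1 and 10.3.5.3. The SAP states no rule for it. One can also argue that a patient removed before any application says nothing about the agent, so counting that patient as a failure is a choice of estimand. That is fair, but a set of all randomised patients analysed by planned treatment already points to that choice.

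Fourth, set membership and missing-data handling are separate rules, both openly stated, so calling them a flat contradiction goes too far. The clearer conflict in the text is that section 10.2 refers to imputation under section 10.1 while the main analysis in 10.1.1 imputes nothing.

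Finally, few such patients are expected: section 10.1.1 anticipates little missing data, and extremities at risk are excluded at entry. This limits the size of the shift and leaves its direction unchanged.

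**Conclusion.** The point holds in a limited form. The main primary analysis does not deliver the all-randomised estimate that sections 9.5 and 11.1.2 promise. Any NexoBrid patient without an end-of-soaking result raises the reported rate above the all-randomised rate.

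The shift is 2.3 points for 3 such patients and 4.0 points for 5, under the assumed 42 successes in 75. It is zero if nobody lacks the assessment. Gel Vehicle, at 0 to 10%, moves little.

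A reader might infer that the primary conclusion is at risk. Under the planning rates it is not: the p-value stays far below 0.05 whichever analysis is main. What is affected is the headline rate and odds ratio.

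**What to change.** 1. In sections 10.1.1 and 11.1.2, make the already planned missing-as-failure analysis the main primary analysis. Every randomised NexoBrid and Gel Vehicle patient without documented complete eschar removal at the end of the last soaking counts as not achieving it.
2. Keep complete-case, missing-as-success and tipping-point as sensitivity analyses.
3. State explicitly that this covers patients stopped during treatment and patients randomised to a topical arm but never treated. Report their number by arm.
4. Align section 7.1.4.1 (stopped patients treated as missing) and section 10.2 (imputation by reference to 10.1) with the revised section 10.1.1.

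The cost is a change of wording and a slightly less favourable reported rate if any such patients occur. Power remains about 98.7% at 75 versus 25 with 5 NexoBrid patients counted as failures, on the assumptions above. No clinical stopping rule changes.

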7.1.5. Concomitant medication and treatment

Concomitant medications will be recorded throughout the study, starting from signing on ICF and will include those prescribed for common burn management practice. Any record should include dose, frequency, route, start and stop date and indication.

Unit of blood transfused (whole blood or blood packed cells) with the appropriate volume will be captured for the entire patient's duration in the study and recorded in the concomitant medications form. Any analgesia and anesthesia administered per subject will be recorded in the eCRFs. Incidence & number of procedures for wound care requiring anesthesia will be analyzed.

7.2. Trial schedule

The healing and care of the burn wound may be divided into the three distinctive phases:

1. Eschar removal treatment phase (until complete eschar removal)
2. Wound management (until complete wound closure)
3. Scar modulation and maturation

These phases are common to the care of all wounds and are well defined in acute wounds such as burns.

In this study, these phases and their treatment strategy are equal for all arms, NexoBrid, SOC, and Gel Vehicle, following the ABA white paper recommendations [24].

The total duration of the study treatment and follow up period of each participating subject is expected to be 25 months: following the Eschar removal procedure, each subject will be followed up weekly (Weeks 1, 2, 3 and 4 etc.) until complete wound closure is achieved and 2 weeks later for wound closure confirmation, for each of the subject's TWs. Long-term follow-up visits will be performed at 1, 3, 6, 12, 18 and 24 months post last wound closure confirmation visit (for details see Table 1).

Table 1: Treatment flow chart - all arms³

If applicable
 * Weekly FU assessments will be performed every 7± 2 days from start of treatment until complete wound closure. Long-term FU will be performed 1,3,6,12,18 and 24 M after last wound closure confirmation.
 **First treatment session will include any procedure for eschar removal: the NexoBrid®/Gel Vehicle/Surgical or non-surgical procedure, as per randomization arm
 ** Procedure can be either surgical or non-surgical. A whole period of continuous dressing changes (from first coverage application to last coverage application) is considered as one non-surgical procedure, assessments should not be repeated for each dressing change; Pre procedures assessments refer only to surgical procedures. Post procedures assessments refer to any surgical procedures and for non-surgical procedure only if it is the last procedure

Parameter	Screening tests	Baseline within 1 h Pre First treatment session - All arms	Topical arms (NexoBrid or Gel Vehicle): (refer to first and second application). S=Soaking, R=Removal	SOC procedures** (including additional procedures in the topical arms)	Daily assessments	Management & Re-admissions ⁴ - surgical procedures assessment	Wound	HD or premature discontinuation visit	Weekly FU*	Long-Term FU (1, 3, 6,12,18 & 24 months)*
Inform Consent signing	X									
Medical history	X									
Burn History ⁵	X									
ConMeds & AEs	X	X	X	X	X	X	X	X	X	X
Physical examination ⁶	X									
Demographic data	X									
Vital Signs	X	X	4h post R	Post S	Post	X				
Pain assessment	X ⁷	X	Post S	Pre and 4h post	X					
Photograph of TWs				Pre & Post		Pre & Post		X	X	

³ This table differs from the corresponding table in the protocol. Minor corrections were performed.

⁴Wound Management will include any, post complete eschar removal additional excisions, Autografts, and donor site data if relevant.

⁵ Data captured will include burn etiology, mechanism of injury, place of injury, treatments prior to admission and general description of the burn wound (anatomical locations and description of the eschar (such as: white, moist, dry, gray, charcoal, etc.), % TBSA assessments and depth

⁶ Physical examination will include height and weight. Height will be taken only once, at screening.
⁷ Photos should be taken after cleansing

Parameter	Screening tests	Baseline within 1 h Pre First treatment session - All arms	Topical arms (NexoBrid or Gel Vehicle): (refer to first and second application). S=Soaking, R=Removal	SOC procedures** (including additional procedures in the topical arms)	Daily assessments	Wound Management & Re-admissions ⁴ , surgical procedures assessment	HD or premature discontinuation visit	Weekly FU*	Long-Term FU (1, 3, 6, 12, 18 & 24 months)*
Clinical assessment of the burn ⁸	X	X	Post S	Post		Post		X	
Local lab - HbA1C, WBC, PhCG	X								
Central lab hematology/ biochemistry tests & Urinalysis	X		4 h Post R	Pre & 4 h Post					
Central lab Hematology							1h pre & 4 h post		
Cleansing including at least 2h soaking)	X	#							
Fluid balance ⁹	X	X		X	X				
Randomization	X			Post S	Pre &Post				
Local lab Wound culture	X		4h Post R	4 h Post					
Local lab Blood culture	X								
12-Lead ECG (if feasible)		60, 40, 20 min pre treatment	During: 0.5, 2, 4h from start of first application only		During: 0.5, 2, 4h from start of first treatment only		12, 24, 48h	week 1	

⁸Clinical assessments will include % TBSA per depth, % eschar removed, % excised, % autografted, % wound epithelialization (TW and donor site, if relevant), % graft take as relevant.

⁹ Daily fluid balance will be monitored for 7 days from injury or until hospital discharge, whichever comes first for patients with catheter.

Statistical Analysis Plan V02 of 15 May 2018

Competence Center for Clinical Trials Bremen

Parameter	Screening tests	Baseline within 1 h Pre First treatment session - All arms	Topical arms (NexoBrid or Gel Vehicle): (refer to first and second application). S=Soaking, R=Removal	SOC procedures** (including additional procedures in the topical arms)	Daily assessments	Wound Management & Re-admissions ⁴ - surgical procedures assessment	HD or premature discontinuation visit	Weekly FU*	Long-Term FU (1, 3, 6, 12, 18 & 24 months)*
PK (for a subset of 32 NexoBrid Pts)		X	During: 0.5, 2, 4h from start of first application		12,24,48, 72h				
Immunogenicity assessment (NexoBrid patients only)		X						weeks 4,8 ¹⁰	Long-term FU: 6, 24
Local lab PTT & INR		X	4 h post R - first application only	4 h post- first treatment only	24,48h				
Circumferential extremity wounds monitoring ¹¹		X	during and post R (4 hours from start)	1h pre & post					
Eschar Removal treatment			X	X	Start and end date , type of primary dressing		Type of primary dressing& frequency		
Coverage									

¹⁰ In case that 8 weekly visit is not performed, this assessment should be taken on the relevant weekly/first visit as close as possible to 8 weeks.

¹¹ The Extremities At Risk (EAR) burns prone to develop BICS will be identified at screening and excluded. Monitoring for the development of EAR in circumferential extremity wounds at the above specified timelines will be done. During each topical application (NexoBrid or gel Vehicle), clinical assessment and SpO₂ monitoring will be done continuously. If such assessment is not practical, direct pressure will be measured every 2 hours from start of eschar removal. Direct pressure will be measured before and after each eschar removal procedure and additional surgical procedures

Parameter	Screening tests	Baseline within 1 h Pre First treatment session - All arms	Topical arms (NexoBrid or Gel Vehicle); (refer to first and second application). S=Soaking, R=Removal arms	SOC procedures** (including additional procedures in the topical arms)	Daily assessments	Wound Management & Re-admissions ⁴ - surgical procedures assessment	HD or premature discontinuation visit	Weekly FU*	Long-Term FU (1, 3, 6, 12, 18 & 24 months)*
Wound closure confirmation ¹²								X	Long-term FU: 1, 3
Cosmesis, Function and Quality Of Life ¹³								X	
Scar-modulating procedures and scar					#			#	
Blood transfusion (units & volume)	#	#	#	#	#	#	#	#	
Histological biopsy	#	#	#	#	#	#	#	#	

¹² Wound closure should be confirmed 2 weeks after the initial wound closure assessment for each TW.

¹³ Cosmesis will be evaluated in donor site scars as well

